10.3. A.1.3 Calculation of Visual Acuity Score

The ETDRS chart will be used to measure the best corrected visual acuity (with glasses or best possible glasses prescription). For the purpose of calculating the visual acuity scores, data will be read starting from the first row and by accumulating the number of letters correctly read until the first instance of row where the number of letters read is <3. This assumes that the contiguous rows between row 1 and the first instance of row with a score of <3 have scores ≥3. If row 1 is non-missing but has a score <3, then data will be read only up to row 1 and the visual acuity score will equal the score of row 1. If row 1 is missing or ND then visual acuity will also be missing. In all other cases data will be read until the row where the score is <3 or ND. Below are some examples of some arbitrary cases for calculating the VA scores:

Dummy SubjID	ETDRS Chart Row	Number of letters Read Correctly (Row Score)	VA Score
101	1	5	Row 1 Score+ Row 2 Score+ Row 3 Score+ Row 4 Score+ Row 5 Score+ Row 6 Score+ Row 7 Score= 5+5+3+5+3+3+2 = 26
	2	5	
	3	3	
	4	5	
	5	3	
	6	3	
	7	2	
	8		
	9		
	10		
	11		
	12		
	13		
	14		
102	1	5	Row 1 Score+ Row 2 Score+ Row 3 Score=5+5+3 = 13
	2	5	
	3	3	
	4	ND	
	5	3	
	6	3	
	7	2	
	8		
	9		
	10		
	11		
	12		
	13		
	14		
103	1	5	Row 1 Score+ Row 2 Score+ Row 3 Score=5+5+3 = 13
	2	5	

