7.1.3. Best Corrected Visual Acuity

The best corrected visual acuity (with glasses or best possible glasses prescription) will be measured using the ETDRS charts. The letters on chart A are read using the right eye and chart B using the left eye.

The subject starts the top of the chart and begins to read down the chart. The subject reads down the chart until they reach a row where a minimum of three letters on a line cannot be read. The subject is scored by how many letters could be correctly identified.

The number of correct letters identified by each eye will be collected into the CRF.

Visual acuity will be measured at Screening (Visit 1), Baseline (Visit 2), Week 6 (Visit 5), and Week 12 (Visit 6) visits, and at Week 15 (Follow-up, Visit 7) visit if deemed necessary. The best corrected visual acuity should be obtained at each scheduled visit or repeat visit. It should not be copied from a previous visit.

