9.4.4. Visual Acuity

Visual acuity (best-corrected, measured using ETDRS charts) is expressed in terms of number of letters correctly identified. Change in visual acuity from baseline to termination will be computed for each subject. Baseline will be defined as the last visual acuity assessment prior to receiving investigational product, and termination will be the visual acuity assessment at the Week 12 visit (or the last available after Day 1 for subjects who terminate early). If acuity was assessed at a repeat visit at termination, the acuity from the repeat test will be used. For each subject, the worst eye (ie, the eye with the greatest decrease in visual acuity) will be used in the analysis. Change in visual acuity will be analyzed for the ITT population using ANCOVA, with treatment and center in the model and the baseline acuity as the covariate.

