Mean Deviation (MD) is a global index of visual field depression. The MD ranges from 0 decibels (dB) (no defect) to about -32 dB (end-stage damage). *Change in mean deviation from baseline to termination will be computed for each subject.* Baseline and all other visits for mean deviation will be based on the visits defined by the central reader and study treatment dates. *Baseline mean deviation will be the average of the two mean deviations from the Baseline visit, and termination will be the mean deviation at the Week 12 visit (or the last post-treatment values available after Day 1 for subjects who terminate early). If a repeat test was done at termination, the mean deviation from the repeat test will be used. For each subject, the worst eye (ie, the eye with the greatest decrease in mean deviation) will be used in the analysis.*

The best corrected visual acuity (with glasses or best possible glasses prescription) will be measured using the Early Treatment Diabetic Retinopathy Study (ETDRS) charts. The letters on chart A are read using the right eye and chart B using the left eye. The subject starts at the top of the chart and begins to read down the chart. The subject reads down the chart until they reach a row where a minimum of three letters on a line cannot be read. The subject is scored by how many letters could be correctly identified. Details of visual acuity scoring have been defined in Appendix A.1.3. Change in visual acuity from baseline to termination will be computed for each subject. Baseline will be defined as the last visual acuity assessment prior to receiving study medication, and termination will be the visual acuity assessment at the Week 12 visit (or the last post-treatment assessment available after Day 1 for subjects who terminate early). If acuity was assessed at a repeat visit at termination, the acuity from the repeat test will be used. For each subject, the worst eye (ie, the eye with the greatest decrease in visual acuity) will be used in the analysis.

Other Safety Endpoints:

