6.4. Covariates

The covariate for Mean Deviation is the baseline MD, which is the average of the two mean deviations from the Baseline visit.

The covariate for Visual Acuity is the baseline visual acuity, defined as the last visual acuity assessment prior to receiving study medication.

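### SAP A.1.3 ends the acuity sum at an ND row even when rows below it carry scores; its example 102 is scored 13, which is 11 to 13 letters too low if the chart procedure was followed

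*SAP*

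**What the plan says.** SAP A.1.3 adds the letters read correctly, row by row, up to and including the first row with fewer than three. For that ordinary case it notes: "This assumes that the contiguous rows between row 1 and the first instance of row with a score of <3 have scores ≥3". It then treats ND in two ways:

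- ND in row 1: "If row 1 is missing or ND then visual acuity will also be missing".
- ND in any lower row: "In all other cases data will be read until the row where the score is <3 or ND".

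Example 102 illustrates the second rule. Row 4 is ND, rows 5 to 7 hold 3, 3 and 2 letters, and the printed score is "Row 1 Score+ Row 2 Score+ Row 3 Score=5+5+3 = 13".

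The procedure at the chart is given in SAP 6.2, and in the same terms in Protocol 7.1.3: "The subject reads down the chart until they reach a row where a minimum of three letters on a line cannot be read".

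The score feeds the secondary endpoint of change in acuity. For each subject, "the worst eye (ie, the eye with the greatest decrease in visual acuity) will be used in the analysis" (Protocol 9.4.4; SAP 6.2 and 8.2.2 agree). The analysis is an ANCOVA in the ITT population, and no margin or decision rule is attached.

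**The concern.** In example 102 the number of letters read in row 4 is unknown, yet the rule returns a definite score. That score is the one obtained by assuming no letter was read in row 4 and that reading should have ended there. The rows recorded below suggest the opposite, because a subject tested as described goes on only after passing a row. The same kind of gap in row 1 is treated as missing.

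The consequence depends on when it happens:

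- **At termination**, an understated score looks like a loss of acuity, and the worst-eye rule tends to choose that eye.
- **At baseline**, an understated score looks like a later gain. The worst-eye rule then tends to choose the other eye, and a true loss in the affected eye can disappear. In a safety study this is the less welcome direction.

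The point is confined to ND with a scored row beneath it. ND below the last row read costs nothing.

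**Working it through.** **1. Reproduce the plan's figures.** The rule is: sum from row 1, include the first row below 3 and stop, stop before an ND row.

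- Example 101: 5+5+3+5+3+3+2 = 26, as printed.
- Example 102: 5+5+3 = 13, as printed.

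**2. Possible totals for example 102.** Five letters per row is assumed. It is the highest row score in the A.1.3 examples, and superseded wording in the SAP amendment log says the same. Put each value in row 4 and apply the ordinary stop rule:

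| Row 4 | Total | Printed 13 is too low by |
|---|---|---|
| 0 | 13 | 0 |
| 1 | 14 | 1 |
| 2 | 15 | 2 |
| 3 | 5+5+3+3+3+3+2 = 24 | 11 |
| 4 | 25 | 12 |
| 5 | 26 | 13 |

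So 13 is the lowest of six values and is right only if row 4 was 0.

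**3. Apply the chart procedure.** Reading stops at the first row with three or more letters not read, that is, at most two of five read. Rows 5 to 7 were read, so under that procedure row 4 had at least 3. Only 24 to 26 remain. Totals of 13 to 15 require that the subject read on past a failed row.

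**4. Size in the analysis (illustrative).** The documents give no variance for acuity. Assume one affected eye among 93 subjects in an arm, SD of change 4 to 6 letters per eye, between-eye correlation ρ from 0 to 0.8, and no true mean change. Let L be the error (11 to 13) and θ = SD × √(2(1−ρ)).

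- Probability that the affected eye is selected at termination: Φ(L/θ). With SD 6, ρ 0 and L 11, θ = 8.49 and Φ(11/8.49) = 0.90. Elsewhere it rises to over 0.99. At baseline the probability is 1 minus this, so below 0.10.
- Shift in that subject's analysed change: expected minimum of the two eyes with the error, less that without it. At SD 6, ρ 0, L 11: −11.39 − (−3.39) = −8.00. At SD 4, ρ 0.8, L 13: −13.00 − (−1.01) = −11.99. The range at termination is 8.0 to 12.0 letters lower.
- Shift in the arm mean at termination: 8.00/93 = 0.09 to 11.99/93 = 0.13 letter.
- The same error at baseline moves the analysed change 1.0 to 3.2 letters toward no loss, or 0.01 to 0.03 on the arm mean. A true loss of 10 letters in that eye would be recorded as −10+11 = +1 to −10+13 = +3.
- Standard error of the treatment difference. The analysed variable is the worst eye, with SD × √(1−(1−ρ)/π). At SD 4, ρ 0 this is 3.30, and 3.30 × √(2/93) = 0.48. At SD 6, ρ 0.8 it is 5.81, giving 0.85.
- Largest ratio of shift to standard error: SD 4, ρ 0, L 13, where 10.76/93 = 0.116 and 0.116/0.484 = 0.24.

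**The case against.** The rule is explicit, pre-specified and illustrated, and A.1.3 is a derivation appendix rather than a data-management plan. Protocol 5.3 breaks the blind only once data issues are resolved, and Protocol sections 10 and 11.1 provide for monitoring against source and investigator review of CRFs. A score beneath an ND row is an evident anomaly. A large drop would also stand out, since Protocol 4.2 excludes eyes worse than 20/25 at entry. A.1.3 describes its cases as arbitrary, so example 102 is no evidence that the pattern occurs. In the text available, ND is not defined and example 103 is cut off.

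Most of this stands, and it lowers both the likelihood and the severity. It does not repair the rule. None of those provisions names the pattern, and whatever survives cleaning is still scored as in example 102.

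A reader might also infer that A.1.3 contradicts itself, because its sentence on contiguous rows would put row 4 at 3 or more. The documents do not support that. The sentence belongs to the ordinary accumulation rule, and ND is dealt with separately afterwards. It is supporting context only.

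**Conclusion.** The point holds as a minor correction. The stated rule gives example 102 the lowest possible total. If the chart procedure was followed, that total is 11 to 13 letters too low. It is not certain to be wrong: 13 to 15 remain possible if a subject read past a failed row.

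A reader might infer that the rule biases the comparison between arms or threatens the trial's safety conclusion. The documents do not support that. The rule applies to both arms alike, the frequency of the pattern is not given, and the primary endpoint and mean deviation do not use this score. One affected eye at termination shifts an arm mean by 0.09 to 0.13 letter, under about 0.25 standard error. These last figures rest on the assumed SD, correlation and single affected eye. What matters more is the individual subject, for whom a false loss may be reported or a true one hidden.

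**What to change.** Amend A.1.3 as follows:

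1. ND ends the sum only when no later row has a recorded score.
2. If a later row has a score, query the ND row before unblinding.
3. If the query is not resolved, set that eye's acuity at that visit to missing, as A.1.3 already does for ND in row 1. Correct example 102 accordingly, and define ND.
4. Apply the existing fallbacks to the affected eye only. At baseline, use its last valid pre-dose assessment. This fits SAP 6.4, where baseline is "defined as the last visual acuity assessment prior to receiving study medication", and a Screening value is available: "Visual acuity will be measured at Screening (Visit 1), Baseline (Visit 2), Week 6 (Visit 5), and Week 12 (Visit 6) visits". The A.1.1 baseline window (day −99 to 1) covers it. At termination, use the last-observation rule of SAP section 7. Keep the other eye's valid Week 12 score. Section 7 and A.1.1 do not define carry-forward for a single eye, so this needs a sentence of its own.
5. As a sensitivity analysis, score the ND row at 3 and at 5 letters (24 and 26 in example 102).

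The cost is a few SAP sentences, one corrected example and a small programming check. The downside is that a few scores become missing or are carried forward, and the two eyes of such a subject may then be compared on values from different visits.

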10.5. A.1.5 Sheehan-Suicidality Tracking Scale (S-STs)

The eight-item S-STs as shown below will be converted to Columbia-Classification Algorithm of Suicide Assessment (C-CASA) codes as described in Table 1.

S-STS

SHEEHAN - SUICIDALITY TRACKING SCALE (LIFETIME ASSESSMENT): (Page 2 of 2)

(Copyright Sheehan DV 2005-2009. All rights reserved.)

INSTRUCTIONS: CHOOSE ONLY ONE ANSWER FOR EACH QUESTION.

PLEASE ENSURE THAT ALL DIMENSIONS OF THE QUESTION ARE TAKEN INTO ACCOUNT IN CHOOSING THE APPROPRIATE RESPONSE (FOR EXAMPLE, TIME FRAME, FREQUENCY AND SEVERITY). THE RESPONSE "NOT AT ALL" TO ANY QUESTION MEANS "NONE" AND MEANS THE THOUGHT OR BEHAVIOR "DID NOT OCCUR AT ALL".

1. Did you ever suffer an accident? (0) No (1) Yes
(this includes taking too much of your medication accidentally).

IF NO, SKIP TO QUESTION 2.
IF YES, GO TO QUESTION 1a:

	Not at all (0)	A little (1)	Moderately (2)	Very (3)	Extremely (4)
--	-------------------	-----------------	-------------------	-------------	------------------

1a. to what extent did you plan or intend to hurt yourself in that accident (either passively or actively)?

					
--	--------------------------	--------------------------	--------------------------	--------------------------	--------------------------

IF THE ANSWER TO QUESTION 1a IS 0 (=Not at all), SKIP TO QUESTION 2.
IF IT IS SCORED ≥ 1, GO TO QUESTION 1b:

1b. Did you intend to die as a result of this accident? (0) No (1) Yes

How seriously did you ever:

	Not at all (0)	A little (1)	Moderately (2)	Very (3)	Extremely (4)
--	-------------------	-----------------	-------------------	-------------	------------------

2. think that you would be better off dead or wish you were dead? | | | | |

3. want to harm yourself or to hurt or to injure yourself? | | | | |

4. think about suicide? | | | | |

5. plan for a suicide? | | | | |

6. take active steps to prepare for a suicide attempt in which you expected or intended to die? | | | | |

7. Did you ever injure yourself on purpose? (0) No (1) Yes
IF NO, SKIP TO QUESTION 8.
IF YES, GO TO QUESTION 7a:

How seriously did you:

	Not at all (0)	A little (1)	Moderately (2)	Very (3)	Extremely (4)
--	-------------------	-----------------	-------------------	-------------	------------------

7a. deliberately injure yourself without intending to kill yourself? | | | | |

8. attempt suicide? | | | | |

Table 1. Universal S-STs Mapping to C-CASA

C-CASA Category	C-CASA Category Number	Eight-item S-STs
Completed Suicide	1	Obtain from SAE
Suicide Attempt	2	'Yes' to Item 1b OR ≥1 to Item 1a and 1b is missing OR ≥1 to Item 8
Preparatory action toward	3	≥1 to Item 6

C-CASA Category	C-CASA Category Number	Eight-item S-STS
imminent suicidal behavior (including interrupted attempt or aborted attempt) Suicidal Ideation	4	≥1 to Item 2 OR ≥1 to Item 3 OR ≥1 to Item 4 OR ≥1 to Item 5
Self-injurious behavior with unknown intent	5	n/a
Not enough information, fatal	6	n/a
Self-injurious behavior without suicidal intent	7	EITHER ≥1 to Item 7a OR ≥1 to Item 1a AND "No' to Item 1b
Other (accidental, psychiatric, other)	8	n/a
Not enough information, non fatal	9	n/a

* Note: C-CASA codes 5, 6, 8, and 9 are not applicable to prospectively collected data.

10.6. A.1.6- Columbia – Suicide Severity Rating Scale (C-SSRS)

The C-SSRS is an interview based rating scale that systematically assesses suicidal ideation and suicidal behavior. [Table 2](#) describes the mapping of C-SSRS to C-CASA categories.

Table 2. C-SSRS Mapped to C-CASA - Suicidality Events and Codes

C-CASA Event Code	C-CASA Event	C-SSRS Response
1	Completed suicide	As captured in the safety database
2	Suicide attempt	“Yes” on “Actual Attempt”
3	Preparatory acts towards imminent suicidal behavior	“Yes” on any of the following: 
 • “Aborted attempt”, or • “Interrupted attempt”, or • “Preparatory Acts or Behavior”
4	Suicidal ideation	“Yes” on any of the following: 
 • “Wish to be dead”, or • “Non-Specific Active Suicidal Thoughts”, or • “Active Suicidal Ideation with Any Methods (Not Plan) without Intent to Act”, or • “Active Suicidal Ideation with Some Intent to Act, without Specific Plan”, or • “Active Suicidal Ideation with Specific Plan and Intent”
7	Self-injurious behavior, no suicidal intent	“Yes” on “Has subject engaged in Non-suicidal Self-Injurious Behavior?”
